Planned study centers and number of subjects have been increased from 20 to approximately 30 centers and from 200 to approximately 300 subjects, respectively.	Number of planned centers and subjects have been increased to evaluate roxadustat dosing (initiation or conversion from ESA) in ESRD patients who are receiving hemodialysis at different dialysis organizations.	Synopsis Figure 2	
Exclusion criterion # 13 updated From: Subject has a diagnosis or suspicion (e.g., complex kidney cyst or Bosniak Category II or higher) of renal cell carcinoma as shown on renal imaging performed within 24 weeks prior to enrollment To: Subject has a diagnosis or suspicion (e.g., complex kidney cyst or Bosniak Category II or higher) of renal cell carcinoma (PI's discretion)	To allow the Principal Investigator to make a determination based on clinical judgement in order to minimize additional clinic visit for renal imaging during current pandemic	Synopsis Section 5.2	
Minor editorial changes (to correct			
typographical errors and to improve			
consistency and clarity)			
Subjects who wish to permanently discontinue roxadustat, after EOT should receive the first ESA dose at least two days after the last roxadustat dose instead of three days.	To correct typographic error	Synopsis Section 4.6 Section 7.4	
Word "estimated" added before "Dry weight in HD subjects" for inclusion # 9	For better clarification and consistency	Synopsis Section 5.1	
Exclusion criteria #24 and #25 were not numbered separately due to formatting error. This is corrected.	To correct formatting error	Synopsis	
Updated the Note to remove the word "post dialysis" for subject's dry weight at enrollment	For better clarification and consistency	Table S2	
Body weight categories for patents initiating roxadustat dosing have been corrected as follows (to align with the synopsis): from \leq 100 kg to \leq 100 kg and from \geq 100 kg to \geq 100 kg	To correct typographic error	Table 2	
Temperature collection requirement added with vital signs for applicable visits	To correct an inadvertent error	Section 7	
Clarified that central Hemoglobin during weeks 12 to 24 should be a part of CBC	For better clarification	Section 7.3.3	

Confidential Page 4 of 69

Protocol FGCL-4592-096 A01

Protocol requirement to perform renal	To align with the revised	Table 4
ultrasound removed from screening visit	Exclusion Criterion # 13	
Sample size determination (width of CI) has	To align with the revised number	Synopsis

NDD-CKD	Non-dialysis dependent chronic kidney disease
NYHA	New York Heart Association
PD	peritoneal dialysis
PH	prolyl hydroxylase
PK	Pharmacokinetics
QW	once weekly
RBC	red blood cell
RR	respiratory rate
RRT	renal replacement therapy
SAE	serious adverse event
SAF	safety analysis set
sBP	systolic blood pressure
TBL	total bilirubin
TEAE	treatment-emergent adverse event
TESAE	treatment-emergent serious adverse event
TIBC	total iron binding capacity
TIW	three times weekly
TSAT	transferrin saturation
UIBC	unsaturated iron binding capacity
ULN	Upper limit of normal
USRDS	United States Renal Data System
VEGF	vascular endothelial growth factor
WBC	white blood cell
Wt	Weight

1. PROTOCOL SYNOPSIS

Study Title:	Phase 3b Multicenter, Open-Label Single Arm Study of Roxadustat: Either as Conversion from an Erythropoiesis Stimulating Agent (ESA), or as Initial		
Protocol Number:	Anemia Treatment in Hemodialysis (HD) Patients - ASPEN Study FGCL-4592-096		
Investigational Product:	Roxadustat (FG-4592)		
Target Population:	Subjects with end-stage renal disease (ESRD) on HD, who either are on a stable ESA dose, or are newly initiating anemia treatment		
IND Number:	074454		
Study Phase:	Phase 3b		
Study Centers Planned:	Approximately 30 sites in the USA		
Number of Subjects Planned:	Approximately 300 subjects		
Primary Objectives:	To confirm safe and effective Roxadustat dosing regimens among in-center HD subjects converted from ESA therapy (>=6 weeks ESA treatment) or who are ESA-naïve (<6 weeks ESA treatment)		
Safety / Exploratory Objectives:	 Assessment of treatment-emergent adverse events (TEAEs) and serious adverse events (TESAEs) Laboratory parameters, including iron indices Utilization of intravenous (IV) iron Dosing compliance To test operational characteristics of converting a population of ESRD subjects from an injectable to oral anemia therapy 		
Study Design Overview:	Single-arm study to evaluate roxadustat in correcting or maintaining Hb in ESRD subjects receiving in-center hemodialysis: • Either after conversion from a stable ESA dose: ESA use ≥ 6 weeks prior to conversion to roxadustat dosing • Or as initial anemia treatment, in subjects with < 6 weeks of ESA use or no prior ESA use prior to start of roxadustat dosing The study periods are as follows: ○ Screening Period: Up to 6 weeks ○ Treatment Period: 24 weeks ○ Post-Treatment Follow-Up Period: Subjects permanently discontinuing roxadustat should have one final safety assessment 28 days after the last roxadustat dose. For subjects converted from an ESA, the initial roxadustat dose is based on the average prescribed ESA dose in the last 4 weeks (8 weeks for Mircera) prior to conversion (See Table S1). Roxadustat treatment should start after the following intervals: • Two days after stopping epoetin		

Confidential Page 12 of 69

- One week after stopping darbepoetin alfa
- Two weeks after stopping methoxy polyethylene glycol-epoetin beta (Mircera®)

For subjects initiating anemia treatment (< 6 weeks of prior ESA use), the initial roxadustat dose is based on estimated dry weight at enrollment (See Table S2).

Roxadustat dose adjustments should follow the Dose Adjustment Rules, to maintain Hb within the target range specified in Table S3).

During the Treatment Period, subjects will attend biweekly study visits from Day 1 to Week 8, followed by every 4-week study visits, from Week 8-24. Local Hb values will be drawn, prior to dialysis, in order to determine the need for a dose adjustment, and to assess for excessive rate of Hb rise, in real-time.

After completing the Treatment Period (Week 24 /EOT), subjects who wish to permanently discontinue roxadustat, should receive the first ESA dose at least two days after the last roxadustat dose. Subjects permanently discontinuing roxadustat should also have one final safety assessment 28 days after the last roxadustat dose.

See Table 4 for the complete Schedule of Assessments.

An extension of roxadustat treatment after 24 weeks may be offered to interested subjects within the context of this study protocol upon agreement of the study site, until roxadustat is commercially available, or up to 1 year after completing the 24 weeks, whichever comes first.

Inclusion Criteria:

A subject is eligible for the study if all of the following criteria are met:

- 1. Subject has been informed of the investigational nature of this study and has given written informed consent in accordance with institutional, local, and national guidelines
- 2. Subject is ≥ 18 years of age
- 3. Receiving in-center hemodialysis for end stage renal disease (ESRD)
- 4. Prior ESA use:
 - For a subject converting from an ESA: On ESA ≥ 6 weeks and the prescribed ESA dose should remain stable (as determined by PI) during the 4 weeks prior to initiating roxadustat treatment
 - Subject is initiating anemia treatment: Defined as: < 6 weeks of prior ESA use or no prior ESA use
- 5. Vascular access must be a functioning native arteriovenous fistula or graft with adequate flow in the opinion of the investigator, or permanent tunneled catheter.
- 6. Screening Hb (based on central lab value; measured within 10 days prior to initiating roxadustat treatment):
 - Subjects converting from an ESA: screening Hb is between 9.0 to 12.0 g/dL
 - Subjects initiating anemia treatment: screening Hb is < 10.0 g/dL

Confidential Page 13 of 69

- 7. Ferritin ≥ 50 ng/mL, Transferrin saturation (TSAT) $\geq 10\%$ at screening (subject may qualify after receiving iron supplement per local standard of care) 8. Subject's alanine aminotransferase (ALT) and aspartate aminotransferase (AST) are ≤ 3 x upper limit of normal (ULN), and total bilirubin (TBL) is ≤ 1.5 x ULN at screening and prior to initiating roxadustat treatment. (TBL up to 2 x ULN may be allowed if AST and ALT are within normal 9. Subject's body weight (estimated dry weight in HD subjects) is 45.0 to 160.0 kgSubjects will be excluded if any of the following criteria are met: **Exclusion** 1. Subject has received a red blood cell (RBC) transfusion within 4 weeks Criteria: prior to enrollment 2. Subject has a known history of myelodysplastic syndrome or multiple myeloma 3. Subject has a known hereditary hematologic disease such as thalassemia or sickle cell anemia, pure red cell aplasia or other known causes for anemia other than chronic kidney disease (CKD) 4. Subject has known hemosiderosis, hemochromatosis, coagulation disorder, or hypercoagulable condition 5. Subject has a known chronic inflammatory disease that is determined by the investigator to be the primary cause of anemia (eg, systemic lupus erythematosus, rheumatoid arthritis, celiac disease) 6. Subject is anticipated to undergo elective surgery that is expected to lead to significant blood loss during the study period or anticipated elective coronary revascularization. 7. Subject has active or chronic gastrointestinal bleeding 8. Subject has been treated with iron-chelating agents within 4 weeks prior to enrollment 9. Subject has a history of chronic liver disease (eg, chronic infectious hepatitis, chronic auto-immune liver disease, cirrhosis, or fibrosis of the 10. Subject with New York Heart Association (NYHA) Class III or IV congestive heart failure 11. Subject has had an MI, acute coronary syndrome, stroke, seizure, or a thrombotic/thromboembolic event (excluding vascular dialysis access stenosis/thrombosis) (eg, DVT or pulmonary embolism) within 12 weeks prior to enrollment 12. Subject has uncontrolled hypertension, in the opinion of the Investigator 13. Subject has a diagnosis or suspicion (e.g., complex kidney cyst or Bosniak Category II or higher) of renal cell carcinoma (PI's discretion) 14. Subject has a history of malignancy, except for the following: cancers determined to be cured or in remission for ≥ 2 years, curatively resected
 - 15. Subject is positive for any of the following:

resected colonic polyps

• Human immunodeficiency virus (HIV)

basal cell or squamous cell skin cancers, cervical cancer in situ, or

- Hepatitis B surface antigen (HBsAg)
- Anti-hepatitis C virus antibody (anti-HCV Ab)
- 16. Subject has an active, clinically significant infection at the time of enrollment as determined by the investigator
- 17. Subject has any of the following known untreated conditions as determined by the investigator: proliferative diabetic retinopathy, diabetic macular edema, macular degeneration or retinal vein occlusion (subjects who are already blind may qualify to participate)
- 18. Subjects with prior organ transplant who have one of the following conditions or states
 - a) Experienced rejection of transplanted organ within 6 months of transplantation
 - b) Currently on high doses of immunosuppressive therapy (per discretion of the investigator)
 - c) Are scheduled for organ transplantation (on the waiting list for kidney transplant is not exclusionary)
- 19. Subject has participated in an interventional clinical study or has been treated with an investigational drug within 4 weeks prior to screening
- 20. Subject has drug-treated gastroparesis, short-bowel syndrome, or any other gastrointestinal condition that may lead to reduced absorption of study drug (determined by the investigator)
- 21. Subject has an anticipated use of dapsone or androgen in any dose amount or anticipated chronic use of acetaminophen or paracetamol > 2.0 g/day during the study
- 22. Subject has a history of alcohol or drug abuse within 6 months prior to screening as determined by the clinical judgment of the investigator
- 23. Females of childbearing potential, if not practicing complete sexual abstinence or using contraception as detailed in the protocol; male subjects (if not surgically sterile; i.e., no vasectomy) with sexual partners of childbearing potential, if not practicing complete sexual abstinence or using contraception
- 24. Pregnant or breastfeeding females
- 25. Subject has any medical condition that in the opinion of the Investigator may pose a safety risk to the subject in this study, which may confound efficacy or safety assessment, or may interfere with study participation

Study Procedures:

See Schedule of Assessments (Table 4)

Investigational Product

Roxadustat tablets are available in 20, 50, 70, 100 and 150 mg doses for oral administration. All tablets must be administered whole.

Route of Administration: Oral (all tablets must be administered whole) **Dosing Frequency:** Subjects will be dosed three times weekly (TIW), except if a subject requires < 60 mg/week to maintain Hb levels, in which case dose frequency may be reduced in a stepwise fashion, e.g., to twice weekly (BIW), then once weekly (QW).

Initial Doses:

• Conversion from ESA to Roxadustat:

Confidential Page 15 of 69

The initial roxadustat dose is determined using a conversion table based on the subject's prescribed ESA dose in the last 4 weeks prior to enrollment (for Mircera[®]:in the last 8 weeks prior to enrollment) (Table S1). Roxadustat treatment should start after the following intervals:

- Two days after stopping epoetin
- One week after stopping darbepoetin alfa
- Two weeks after stopping methoxy polyethylene glycol-epoetin beta (Mircera®)

If the converted initial dose exceeds the maximum dose of 3.0 mg/kg/dose then the next-lower dose step should be chosen as the initial dose. If a subject is on ESA dose hold for high haemoglobin during screening, enrollment should be delayed until the subject is ready to resume anaemia treatment. Upon enrollment, all subjects must initiate roxadustat at Day 1.

Table S1: Conversion from ESA to Roxadustat

Previous dose of Darbepoetin alfa (mcg/week)	Previous Dose of Epoetin alfa (IU/week)	Previous Dose of Mircera® (mcg/month)	Starting Dose of Roxadustat (mg/dose TIW)
<25	< 5000	<80	70
25 to 40	5000 to 8000	80 to 120	100
>40	>8000	>120	150

• Initiation of Roxadustat in subjects with < 6 weeks of prior ESA

Initial roxadustat dosing is based on broad body weight categories (estimated dry weight at enrollment):

Table S2: Initial Roxadustat Dosing:

Body Weight Category	< 100 kg	≥ 100 kg
Roxadustat Dose (TIW)	70 mg	100 mg

Note: Weight in HD subjects = subject's estimated dry weight at enrollment.

Dose Adjustments:

During the Treatment Period, roxadustat dose adjustment will be made starting at Week 4 and at intervals of every 4 weeks thereafter according to the dose adjustment algorithm below, in order to achieve an Hb level of 11 g/dL and maintain an Hb of 11 ± 1 g/dL:

Confidential Page 16 of 69

Table S3: Dose Adjustments:

		Current Hb level:			
		<10.5 g/dL	10.5 to 11.9 g/dL	12.0 to 12.9 g/dL	≥13.0 g/dL
b over eeks:	> 1.0 g/dL	No change	ļ	↓	Hold dosing Check Hb and resume dosing when Hb <12.0 g/dL, at a dose reduced by 2 steps
Change in Hb over previous 4 weeks:	-1.0 g/dL to +1.0 g/dL	↑	No change	1	
Chaı	<-1.0 g/dL	↑		No change*	

^{↑:} Increase dose by one step; ↓: reduce dose by one step.

Dose adjustment steps: 20, 40, 50, 70, 100, 150, 200, 250, 300 and 400 mg

If Hb increases by >2.0 g/dL within a 4-week period, reduce dose by one step.

Roxadustat dose adjustment reviews should occur every 4 weeks, except if the following criteria are met:

- Rate of Hb rise > 2 g/dL within 4 weeks: reduce dose by 1 dose step
- Hb level ≥ 13g/dL: hold dose, check Hb weekly or as deemed necessary by investigator until Hb drops to < 12g/dL, resume dosing at 2 dose steps lower

Dose adjustments or temporary dose holds for excessive rate of Hb rise or Hb above 13 g/dL can occur at any time during the Treatment Period. Any dose adjustment will reset the dose-adjustment window to every 4 weeks thereafter (e.g., dose adjustment for a qualified reason at Week 6 leads to next dose adjustment at Week 10).

Prescribed dose must not exceed the maximum allowable dose of 3.0 mg/kg/dose or 400 mg per dose, whichever is lower. Estimated dryweight at enrollment should be used for the entire treatment period.

Rescue Therapy and Emergency Procedures:

Rescue Therapy Guidelines:

Rescue therapy guidelines are provided to optimize the standardization of rescue therapy, and to ensure the safety of individual study subjects.

Red Blood Cell Transfusion (for all subjects)

RBC transfusion should be considered if rapid correction of anemia is required to stabilize the subject's condition (e.g., acute hemorrhage) or the Investigator is of the opinion that the blood transfusion is a medical necessity. If the situation permits, the Medical Monitor should be informed prior to any scheduled RBC transfusion. Study treatment may continue during or after the RBC transfusion.

Erythropoiesis Stimulating Agent (ESA) Use

If possible, the use of ESAs as a "Rescue" modality should be carefully considered, and should be restricted to no more than one cycle of use during the Treatment Period; the Investigator may initiate use of an approved erythropoietin (EPO) analogue if all of the following criteria are met:

Confidential Page 17 of 69

^{*}Continue to hold dose

A subject's Hb level has not sufficiently responded to two or more dose increases or the maximum dose of study drug has been reached, The subject's Hb is ≤ 8.5 g/dL on two consecutive measurements (central lab) drawn at least five days apart; and Clinical judgment does not suggest iron deficiency or bleeding as a cause of lack of response or rapid decline in Hb, and Reducing the risk of alloimmunization in transplant eligible subjects and/or reduction of other RBC transfusion-related risks is a goal Such ESA Rescue should be started ≥ 2 days after the last dose of roxadustat. ESA Rescue should be stopped when Hb > 9 g/dL or after 4-weeks, whichever comes first. If a subject requires longer than 4-weeks therapy due to inadequate response, or in other extenuating circumstances, the Medical Monitor should be contacted. Study treatment should be resumed after the following intervals: Two days after stopping epoetin • One week after stopping darbepoetin alfa Two weeks after stopping methoxy polyethylene glycol-epoetin beta (Mircera®) If more than one cycle of ESA rescue is required, the Investigator should permanently discontinue study drug. Inadvertent ESA administration, such as ESA administration during a hospitalization, should not be counted as rescue unless above criteria are met; these subjects may be allowed to restart roxadustat dosing if considered safe by the Investigator or Medical Monitor. All ESAs used during the Treatment Period, either planned or inadvertent, should be recorded. ESAs and Roxadustat should not be administered concomitantly. **Emergency Procedure (Therapeutic Phlebotomy)** If there are clinical concerns for a subject's high Hb levels, the Investigator may decide to perform a therapeutic phlebotomy in addition to temporarily withholding the study drug. This should be documented and discussed with the Medical Monitor. IV Iron Use: **Intravenous Iron Supplementation** Intravenous iron should be considered for subjects with ferritin <100 ng/mL or TSAT <20%. IV iron should administered in 5 doses of 50 mg/dose. Medical Monitor should be contacted if more IV iron is required. In this study, oral iron may be administered for iron supplementation without restriction. Dose and frequency of administration of oral iron are to be determined by the investigator. **Prohibited** The following medications/therapies are prohibited during the period **Medication:** identified: Any investigational drug from 4 weeks prior to screening until EOS Androgens from screening until EOS

Confidential Page 18 of 69

Protocol FGCL-4592-096 A01

Roxadustat	Protocol FGCL-4392-090 A01	
	 Iron-chelating agents (e.g., deferoxamine/desferrioxamine, deferiprone, or deferasirox therapy) from 4 weeks prior to enrollment until EOS Dapsone (at any dose) from screening until EOS Chronic doses acetaminophen/paracetamol > 2.0 g/day from enrollment until 1 week after EOT 	
Efficacy	Efficacy Endpoints:	
Endpoints and Assessments:	 Proportion of subjects with mean Hb ≥ 10g/dL, averaged from Week 16 through Week 24 	
	 Mean Hb change from baseline to average Hb from Week 16-Week 24 	
	Exploratory Endpoints/Analyses:	
	Time to first RBC transfusion	
	 Proportion of patients with a mean Hb levels ≥10 g/dL in the first 8 weeks after conversion 	
	• Proportion of patients with a mean Hb level ≥10 g/dL based on	
	baseline ESA use status (≥ 6 weeks and < 6 weeks)	
	• Evaluate the utilization of intravenous (IV) iron (IV iron use/4 weeks)	
	 Evaluate the effect on iron indices 	
	Evaluate dosing adherence	
	• Conversion subjects:	
	 Comparison of starting dose of roxadustat to roxadustat dose at Week 16-24 	
	Mean number of dose adjustments during study	
Safety	Study-specific safety will be assessed by evaluating the following:	
Assessments and	• Incidence of treatment emergent adverse events (TEAEs) and	
Endpoints:	treatment emergent serious adverse events (TESAEs)	
	Clinically significant changes in laboratory values from baseline	
	• Vital signs	
Statistical	Stratification: Not applicable	
Methods:	Sample size determination:	
	Approximately 300 subjects with anemia of CKD (either with or without	
	treatment with ESA at enrollment) and on hemodialysis are planned in this	
	study. This number of subjects distributed across the specified number of	
	sites is adequate to evaluate the primary study objective.	
	Assuming the proportion of subjects that maintain Hb levels ≥10g/dL from	
	Weeks 16-24 is at least 80%, with a sample size of 300, the study will be	
	able to produce a two-sided 95% confidence interval (CI) with a width equal of 9.5%.	
	Analysis Sets:	
	The FAS set will consist of all subjects who signed informed consent, who	
	were enrolled, and who provided baseline Hb data and data for at least one post baseline Hb time point. The FAS set will be used for all efficacy	
	endpoints and analyses.	

Confidential Page 19 of 69

The Safety analysis set will include all enrolled subjects receiving at least 1 dose of study treatment. The safety analysis set will be used for all safety endpoints and exposure to study treatment outcomes.

Efficacy analyses:

The efficacy endpoint will be evaluated using the proportion (%) of subjects with mean value of Hb measurements of ≥ 10 g/dL from Week 16 through Week 24.

For the efficacy analysis, a multiple imputation (MI) method will be used. This will be implemented on the raw Hb values, then the endpoint will be derived based on the imputed data (algorithm as used for the previous phase 3 studies).

For continuous endpoints, changes from baseline will be presented descriptively.

Proportion of responders will be presented descriptively with count and percentages and 95% confidence interval of the responder rate.

Time to response will be analyzed using the Kaplan-Meier method with KM curve plotted.

Safety:

The safety analyses will be performed using the Safety Analysis Set (SAF). Safety parameters include TEAEs, TESAEs, laboratory parameters and vital signs.

The number and percentage of subjects reporting treatment-emergent AEs (TEAEs) and TESAEs will be tabulated.

Descriptive statistics will be presented for laboratories and vital signs.

This study will be conducted in accordance with the guidelines of Good Clinical Practice and the applicable regulatory requirement(s), including the archiving of essential documents.

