7.3.2. Weeks 2 to 8 (Every 2 Weeks, ± 4 days)

- Vital signs (BP, HR, temperature)
- Laboratory tests:
 - o Hemoglobin (central and local lab)
 - Draw a central Hb only on visits CBC is not collected
- Week 4 and Week 8:
 - o Complete blood count (CBC) with WBC differential
 - o Serum chemistry
- Week 8:
 - o CPK
 - Serum iron, ferritin, total iron-binding capacity (TIBC), transferrin saturation (TSAT),
 Reticulocyte count and hemoglobin in reticulocytes (CHr)
- Dose review at every visit and dose adjustment every 4 weeks
- TEAE/CM recording
- Study drug dispensing

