9.2. Analysis Sets

The FAS set will consist of all subjects who signed informed consent, who were enrolled, and who provided baseline Hb data and data for at least one post baseline Hb time point. The FAS set will be used for all efficacy endpoints.

The Safety analysis set will include all enrolled subjects receiving at least 1 dose of study treatment. The safety analysis set will be used for all safety endpoints and exposure to study treatment outcomes.

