5.3.2 Full Analysis Set (FAS)

The FAS set will consist of all subjects who signed the informed consent, were enrolled, and provided baseline Hb data and data for at least one post baseline Hb time point. The FAS set will be used for all efficacy endpoints.

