9 EFFICACY ANALYSES

Efficacy analysis will be conducted on the FAS population.

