9.1 ANALYSIS OF EFFICACY ENDPOINTS

9.1.1 Proportion of subjects with mean Hb ≥ 10 g/dL, averaged from Week 16 to Week 24

The efficacy endpoint will be evaluated using the proportion (%) of subjects with mean value of Hb measurements from Week 16 to Week 24 ≥ 10 g/dL.

Proportion of responders will be presented descriptively with counts and percentages and a 95% confidence interval of the responder rate. The 95% CI of the response rate will be presented based on normal approximation.

For the Hb efficacy analysis, a multiple imputation (MI) method will be used. This will be implemented on the raw Hb values, then the Hb-relates endpoint summaries will be derived based on the imputed data (algorithm as used for the previous phase 3 studies).

The following steps will be used to conduct the MI procedure of the Hb values:

1. Generate 200 datasets, using seed 12345, where only intermittent missing Hb data will be imputed relying on non-missing data from all subjects using the Monte Carlo Markov Chain (MCMC) imputation model using baseline Hb and the available non missing Hb for each scheduled week.

The MCMC statement in the SAS PROC MI procedure with monotone option will be used. As a result, each dataset will only have missing ending data, or a monotone missing data pattern.

2. For each dataset from step 1, missing ending data (Hb up through end of evaluation period) will be imputed. As a result, 200 imputed complete datasets will be generated.

- Missing data at Week 2 will be imputed using the regression imputation model with baseline and Hb from Week 2, using the SAS PROC MI procedure with the REGRESSION option in the MONOTONE statement.
- Repeat for all other scheduled weeks sequentially (Week 4 to the end of evaluation period). Subjects whose missing data were imputed for previous weeks will contribute to the imputation for the current week.
- The regression imputation model includes an intercept and the slopes of the Hb from previous weeks.

Steps 3 and 4 will be used to analyze proportion of subjects with a mean Hb level ≥ 10 g/dL, averaged from Week 16 to Week 24 using the imputed Hb data above:

3. Analyze each imputed complete dataset to estimate proportions of responders and their standard errors using the mean of all observed or imputed Hb values within the evaluation period (Weeks 16 to 24).

Sample SAS code:

```
PROC FREQ DATA=xx;
  TABLES resp_week16_24 / cl binomial (level=2);
  BY _Imputation_;
  ODS OUTPUT BINOMIALPROP=prop;
RUN;
```

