9.2 ANALYSIS OF EXPLORATORY ENDPOINTS

The analysis for the exploratory endpoints will be based on the FAS population.

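### The FAS requires a post-baseline Hb, so a few dosed subjects with none drop out of the responder rate and out of time to first RBC transfusion, which can then miss early events

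*Protocol*

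**What the plan says.** The entry rule is the same in both documents. The protocol (Synopsis and 9.2) asks for consent, enrollment and a subject "who provided baseline Hb data and data for at least one post baseline Hb time point". SAP 5.3.2 repeats it: "provided baseline Hb data and data for at least one post baseline Hb time point".

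The set is applied widely. Protocol 9.2: "The FAS set will be used for all efficacy endpoints". SAP 9: "Efficacy analysis will be conducted on the FAS population". SAP 9.2: "The analysis for the exploratory endpoints will be based on the FAS population". That last section includes time to first RBC transfusion (SAP 9.2.1), whose clock starts at the first dose.

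The only set that keeps every dosed subject is the Safety set: "The Safety analysis set will include all enrolled subjects receiving at least 1 dose of study treatment". It is not used for the responder rate or the transfusion endpoints.

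The first scheduled post-baseline Hb is at Week 2, ±4 days (Protocol 7.3.2). SAP 5.1 uses central laboratory values only for efficacy, so I read the qualifying Hb as a central one, although the FAS definition does not say so.

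**The concern.** Membership of the efficacy set depends on something that happens after treatment starts. In a single-arm study the responder rate is itself the result, and no control arm shares the same selection.

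The method does not need the restriction. The imputation in SAP 9.1.1 can start from baseline alone: "Missing data at Week 2 will be imputed using the regression imputation model with baseline". Time to first transfusion needs no Hb at all. For that endpoint, follow-up counts from Day 1 while entry depends on a later blood draw. A subject transfused on Day 5 who dies on Day 8 with no Hb drawn has a transfusion during time at risk, yet never enters the curve.

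At stake are a possible overstatement of the Hb response and an undercount of the earliest transfusions.

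**Working it through.** **Who is lost**

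- The scheduled Week 2 day is 7 × 2 + 1 = Day 15, so the draw falls on Days 11 to 19. The SAP window for Week 2 is wider, Days 2 to 21 (SAP Table 5).
- Subjects who stop are due a visit with a CBC 28 days after the last dose (Protocol 7.4). A subject stopping on Day 5 is due on Day 33, ±7 days (Days 26 to 40). That falls in the Week 4 window (Days 22 to 35) or the Week 6 window (Days 36 to 49), so it supplies a post-baseline Hb.
- SAP Table 5 also maps the last early-termination assessment from Day 2 onward to a scheduled visit.
- So only subjects with no Hb at all from Day 2 are lost. Protocol 5.3 asks for the 28-day follow-up where feasible. Death, loss to follow-up and withdrawal of consent are the main ways it would not happen.

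**The plan's own figure**

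The sample-size sections state a 95% CI width of 9.5% at a rate of 80% with 300 subjects. For 240/300:

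- Clopper-Pearson (Protocol 9.3): 75.02% to 84.38%, width 9.36 points, close to the stated figure.
- Normal approximation (SAP 9.1.1): 2 × 1.96 × √(0.80 × 0.20 / 300) = 9.05 points.

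The half-width is therefore about 4.5 to 4.7 points.

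**Responder rate**

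Let k be the number of dosed subjects excluded out of 300 and q their response rate, with an FAS rate of 80%.

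- All-dosed rate = 0.80 × (300 − k)/300 + q × k/300
- Inflation of the FAS rate = (0.80 − q) × k/300

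The documents do not give k; 1% to 5% is an assumed range.

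| k (share) | All-dosed rate, q = 0 | Inflation, q = 0 | Inflation, q = 0.5 | Inflation, q = 0.8 |
|---|---|---|---|---|
| 3 (1%) | 79.2% | 0.8 points | 0.3 | 0 |
| 6 (2%) | 78.4% | 1.6 | 0.6 | 0 |
| 9 (3%) | 77.6% | 2.4 | 0.9 | 0 |
| 15 (5%) | 76.0% | 4.0 | 1.5 | 0 |

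The last column approximates adding these subjects and imputing them under SAP 9.1.1, if their baseline Hb resembles that of the others.

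**A rough anchor for k**

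Protocol 2.1.1 gives a life expectancy of 5.9 years on dialysis. At a constant hazard, deaths by Day 19 are 1 − exp(−19/(365.25 × 5.9)) = 0.88%, or about 2.6 of 300. That figure is for dialysis patients in general; the exclusion criteria (NYHA class III–IV, recent MI or stroke, active infection) probably lower it here.

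**Transfusion endpoints**

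Assume, for illustration, 15 subjects with an event in the FAS and 3 subjects excluded (crude proportions):

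| Endpoint | FAS | All dosed |
|---|---|---|
| Any transfusion from first dose, all 3 excluded transfused early | 15/297 = 5.05% | 18/300 = 6.00% |
| Same, 1 of the 3 transfused | 15/297 = 5.05% | 16/300 = 5.33% |
| Transfusion from Day 29 to Week 24 (SAP 9.2.8) | 15/297 = 5.05% | 15/300 = 5.00% |

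In the last row early events do not count in either set, so the exclusion only shrinks the denominator.

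**The case against.** The strongest reply is that few subjects are affected and the plan already shows who they are. Stopping drug does not by itself remove anyone, because the 28-day CBC and the mapping in SAP Table 5 usually supply an Hb. Study drug may continue after a transfusion (Protocol 4.7.3.1). SAP 6 reports the size of each analysis set and discontinuations by reason in the enrolled population, and deaths and SAEs are reported on all dosed subjects. No hypothesis is tested, and the transfusion endpoints are exploratory. All of this stands, and it limits the size of the problem.

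The reply also disposes of three stronger readings that a reader might infer:

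- *Everyone who stops or is transfused before Week 2 is removed.* The early-termination provisions contradict this.
- *The bias runs one way across all efficacy endpoints.* It does not for the SAP 9.2.8 proportions, where exclusion slightly raises the rate. For the responder rate it depends on how the excluded subjects would have done. Transfer to another center, transplant and site closure are also listed reasons for stopping (Protocol 5.3), and scheduled dose adjustment starts only at Week 4, so leaving before Week 2 is weak evidence of Hb non-response.
- *The FAS rule alone inflates the responder rate by 0.8 to 4.0 points.* That range needs both an assumed 1% to 5% exclusion and a rule scoring those subjects as failures. Adding them under the planned imputation would leave the rate near 80%.

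Non-responder scoring as the main analysis would also sit awkwardly with the plan: a subject leaving in Week 1 would be a failure, while one leaving after a Week 2 Hb is imputed.

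The reply does not answer the time-to-first-transfusion problem, and no all-dosed analysis of the responder rate is planned.

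**Conclusion.** The point holds in a limited form. Dosed subjects with no post-baseline Hb leave the responder rate and time to first RBC transfusion. For time to first transfusion the restriction serves no purpose and can drop early events, whatever view is taken of missing Hb.

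For the responder rate, the inflation is at most 0.8 points per 1% of dosed subjects excluded, reached only if every excluded subject is a failure. The mortality anchor suggests the low end, about 1% or less from deaths, against a CI half-width of about 4.5 to 4.7 points; losses to follow-up and withdrawals would add to that by an unknown amount. These figures rest on an FAS rate of 80%, 300 dosed subjects and an assumed exclusion share.

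The documents do not support replacing the main efficacy population, and the SAP 9.2.8 proportions need no change on this ground.

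One point stays open. SAP 4.2 censors Hb for 4 weeks after a transfusion, and neither document says whether a censored value still qualifies a subject for the FAS. If it does not, early-transfused subjects could be lost as well.

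**What to change.** 1. SAP 9.2.1: analyse time to first RBC transfusion on the Safety set. Because Protocol 9.2 assigns the FAS to all efficacy endpoints, record this as a stated exception.
2. SAP 9.1.1: keep the FAS analysis as planned, and add a sensitivity analysis of the Week 16–24 responder rate in all dosed subjects with a baseline Hb, counting those with no post-baseline Hb as non-responders.
3. SAP 5.3.2: state whether an Hb censored after a transfusion qualifies a subject for the FAS.

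The cost is a few sentences and one extra table. The downside is a responder rate that may be slightly lower in the sensitivity analysis.
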